**Table 10: Correlative and Required Send out Sample Schedule:**

Sample Time Point	Container 	Sample Type	Shipping Method	Recipient
Baseline or C1D1 Predose	6x6mL Green 1x6ml Red	Peripheral Blood	Hand-delivered or Fridge pack overnight shipping	Brown Lab
	1x6ml Green	Bone Marrow Aspirate	Hand-delivered or Fridge pack overnight shipping	Brown Lab
	MUTATIONS	Peripheral Blood	Ambient	Mayo Clinic or Local Assay
	1x Oragene Kit	Saliva 	Ambient	Brown Lab
C1D8 Predose	6x6mL Green 1x6ml Red	Peripheral Blood	Hand-delivered or Fridge pack overnight shipping	Brown Lab
C2D1	6x6mL Green 1x6ml Red	Peripheral Blood	Hand-delivered or Fridge pack overnight shipping	Brown Lab
C4D1	1x6ml Lavender	Peripheral Blood	Ambient	Mayo Clinic MRD
	6x6mL Green 1x6ml Red	Peripheral Blood	Hand-delivered or Fridge pack overnight shipping	Brown Lab
C7D1, C13D1, C25D1	6x6mL Green 1x6ml Red	Peripheral Blood	Hand-delivered or Fridge pack overnight shipping	Brown Lab
	1x6ml Green	Bone marrow Aspirate		
	1x6ml Lavender	Bone marrow Aspirate	Ambient	Mayo Clinic MRD
	1x6ml Lavender	Peripheral Blood	Ambient	Mayo Clinic MRD

CONFIDENTIAL

This document is confidential. Do not disclose or use except as authorized.

C11D1	1x6ml Lavender	Peripheral Blood	Ambient	Mayo Clinic MRD
C16D1	1x6ml Lavender	Peripheral Blood	Ambient	Mayo Clinic MRD
C19D1	6x6mL Green 1x6ml Red	Peripheral Blood	Hand-delivered or Fridge pack overnight shipping	Brown Lab
Clinically Indicated	1x6ml Green	Bone marrow Aspirate	Hand-delivered or Fridge pack overnight shipping	Brown Lab
	1x6mL Lavender	Bone Marrow Aspirate	Ambient	Mayo Clinic MRD
Confirmation of Complete Response	6x 6mL Green 1x6ml Red	Peripheral Blood	Hand-delivered or Fridge pack overnight shipping	Brown Lab
	1x6ml Green 	Bone Marrow Aspirate	Hand-delivered or Fridge pack overnight shipping	Brown Lab
	1x6mL Lavender 	Bone Marrow Aspirate	Ambient	Mayo Clinic MRD
	1x6ml Lavender	Peripheral Blood	Ambient	Mayo Clinic MRD
End of Treatment or Suspected Progression  OR  Prior to Resuming Venetoclax after Discontinuation	6x6mL Green 1x6ml Red	Peripheral Blood	Hand-delivered or Fridge pack overnight shipping	Brown Lab
	1x6ml Green	Bone Marrow Aspirate	Hand-delivered or Fridge pack overnight shipping	Brown Lab
	1x6mL Lavender	Bone Marrow Aspirate	Hand-delivered or Fridge pack overnight shipping	Mayo Clinic MRD

CONFIDENTIAL

This document is confidential. Do not disclose or use except as authorized.

Every 3 Cycles from C25D1 through C60^6	1x6ml Lavender	Peripheral Blood	Ambient	Mayo Clinic MRD
Every 6 Cycles from Cycle 25 onward	6x6mL Green 1x6ml Red	Peripheral Blood	Hand-delivered or Fridge pack overnight shipping	Brown Lab
Active Disease Monitoring Every 3 months	1x6ml Lavender 	Peripheral Blood	Ambient	Mayo Clinic MRD

Local samples from DFCI, MGH, or BIDMC will be refrigerated and hand-delivered as soon as possible same day to [name] lab- For external investigative sites, shipping instructions are in [section 9](#). Samples are to be shipped to the Brown lab by overnight, trackable shipping on fridge packs

Green=Sodium Heparin Tube; Red= No additive; Purple = K2EDTA; Oragene saliva collection kit provided by lead site and can be collected at any time before or during the trial

 Requisition form for Mayo Labs and for [name] lab provided by the lead site project manager

 Only required in patients who had a positive marrow at baseline

 After C25 (both patients on treatment or in active follow up) bone marrow aspirate samples will be collected each time a bone marrow biopsy is done as part of routine standard of care or the investigator’s discretion

 MRD testing of the peripheral blood will be sent to Mayo Clinic Laboratory just prior to cycles 4, 7, 11, 13, 16, 19, 22, 25 and every three cycles until cycle 60, then at minimum q6 cycles thereafter – During active follow up, MRD of the blood should be tested q3 months or at minimum, q6 months for up to one year.

 Correlative samples requested for all patients who remain on study past cycle 25, i.e. 30, 36, 42, 48, 54, and 60 to be sent to Brown Lab at DFCI.

 Both blood and aspirate MRD samples are to be sent ambient, priority overnight to Mayo Clinic Laboratories at the address listed in section [9.3.2](#)

 Please refer to [section 5.6](#) for full details on active disease monitoring and follow up

CONFIDENTIAL

This document is confidential. Do not disclose or use except as authorized.

## **11. MEASUREMENT OF EFFECT**

### **11.1 Definitions:**

Evaluable for toxicity: All participants who receive at least one dose of study treatment will be evaluable for toxicity from the time of their first treatment.

Evaluable for DLT: All participants who complete the first cycle of combination therapy will be evaluable for DLT from the time of their first treatment. Any patient who experiences a DLT after receiving at least one dose of combination study treatment will also be considered evaluable for DLT. In the phase I portion of the study, if a patient comes off study due to a reason other than a DLT (e.g. disease progression) prior to the end of the DLT observation period, that patient can be replaced.

Evaluable for objective response: Only those participants who have measurable disease present at baseline, have received at least one cycle of therapy, and have had their disease re-evaluated will be considered evaluable for response. These participants will have their response classified according to the definitions stated below. (Note: Participants who exhibit objective disease progression or die prior to the end of cycle 1 will also be considered evaluable.)

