## **5.1 Treatment Regimen**

### **5.1.1 Duvelisib:**

Duvelisib will be administered twice daily, with 28 consecutive days defined as a treatment cycle (up to 49 days for cycle 1), for up to a total of 12 cycles. Treatment will be administered on an outpatient basis with the exception of doses given while inpatient for venetoclax ramp up/dose escalation. Appropriate dose modifications are described in Section 6. Reported adverse events and potential risks are described in Section 7. No investigational or commercial agents or therapies other than those described below may be administered with the intent to treat the participant's malignancy.

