### **5.1.2 Venetoclax:**

Venetoclax will be administered daily, with 28 consecutive days defined as a treatment cycle (up to 42 days for cycle 1) until the time of disease progression without clinical benefit, death, unacceptable toxicity, withdrawal of consent, or physician/patient discussion of discontinuation based on objective disease response, or they elect to go on a new CLL or Richter's directed therapy. The first dose of venetoclax will be given on day 8 of cycle 1 at a starting dose of 10 mg. All patients will be admitted for administration of the initial dose of venetoclax at each dose escalation. Patients will be started on allopurinol and IV hydration for TLS prophylaxis. TLS laboratories will be checked approximately 4, 8, 12, and 24 hours post venetoclax dose. Pre-dose laboratory values will be used as baseline to assess for potential electrolyte abnormalities following venetoclax. Patients can be discharged if no evidence of laboratory TLS 24 hours after dosing, according to the Cairo-Bishop criteria for TLS. If laboratory or clinical TLS is seen, as defined by Cairo-Bishop criteria, patients will be managed as per appendix C. Patients will be admitted weekly for each dose escalation (10 mg, 20 mg, 50 mg, 100 mg, 200 mg, 400 mg) for up to six weeks (42 days) depending on the target dose level. The same rules and TLS laboratory evaluations will be applied for each dose escalation, with the potential to escalate to 100 mg (dose level +1), 200 mg (dose level +2), and 400 mg (dose level +3).

CONFIDENTIAL

This document is confidential. Do not disclose or use except as authorized.

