### 5.3 Definition of Dose-Limiting Toxicity (DLT)

Dose-limiting toxicity (DLT) is based on the CTEP Active Version of the NCI Common Terminology Criteria for Adverse Events (CTCAE) Version 5.0. DLT refers to toxicities experienced at any time during the first cycle of study treatment, defined as the following:

- Grade 4 neutropenia lasting more than 5 days
- Febrile neutropenia of any duration ( $ANC < 1.0 \times 10^9/L$  and fever  $\geq 38.5^\circ F$ )
- Grade  $\geq 3$  thrombocytopenia with clinically significant bleeding
- Grade  $\geq 4$  infection by NCI-CTCAE criteria
- Any grade 3 or greater non-hematologic toxicity with the following exceptions:
  - Grade 3 or greater nausea/vomiting/diarrhea that persists for 7 days or less
  - Grade 3 asymptomatic laboratory abnormalities that improve to grade 2 or less within 3 days
- Any grade  $\geq 3$  diarrhea or vomiting or diarrhea that requires tube feeding, total parenteral nutrition, or requires or prolongs hospitalization
- Inability to receive Day 1 therapy of Cycle 2 after a delay in treatment of up to 21 days due to continued drug related toxicity from the prior cycle
- Severe cutaneous reaction (grade 3 or greater)
- Grade 4 elevation in ALT and/or AST or grade  $\geq 3$  elevation in ALT and/or AST occurring in the context of a Grade  $\geq 2$  elevation in bilirubin
- Grade 5 treatment-related adverse events

All toxicities will be considered relevant to determining DLTs and to reporting unless the event can clearly be determined to be unrelated to the study drug(s).

The DLT observation period is considered the period from the first dose of combination therapy through the completion of cycle 1. In the phase I study, if a patient comes off study due to a reason other than a DLT (e.g. disease progression) prior to the end of the DLT observation period, that patient can be replaced.

CONFIDENTIAL

This document is confidential. Do not disclose or use except as authorized.

Management and dose modifications associated with the above adverse events are outlined in Section 6.

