### **13.4 Reporting and Exclusions**

Participants who never start combination therapy will be excluded from analysis in both the phase I and phase II study

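### Section 11.1 lets a phase I patient count as DLT-free at an assigned venetoclax dose that was never reached, so the DLT rate behind the MTD can be diluted

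*Combined protocol and SAP*

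**What the plan says.** Section 11.1 gives two routes to being evaluable for DLT. The first is completion of the cycle: "All participants who complete the first cycle of combination therapy will be evaluable for DLT from the time of their first treatment". The second is an event: "Any patient who experiences a DLT after receiving at least one dose of combination study treatment will also be considered evaluable for DLT". Section 5.3 sets the window: "The DLT observation period is considered the period from the first dose of combination therapy through the completion of cycle 1".

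Replacement in phase I (sections 5.3, 11.1 and 13.1) applies "if a patient comes off study due to a reason other than a DLT (e.g. disease progression") before the window ends. Section 13.4 removes only one further group: "Participants who never start combination therapy will be excluded from analysis in both the phase I and phase II study".

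Cycle 1 is lengthened to hold the weekly ramp-up. For duvelisib, section 5.1.1 says "with 28 consecutive days defined as a treatment cycle (up to 49 days for cycle 1"); for venetoclax, section 5.1.2 says "28 consecutive days defined as a treatment cycle (up to 42 days for cycle 1"). Section 5.1.2 plans weekly steps of 10, 20, 50, 100, 200 and 400 mg from day 8, "for up to six weeks (42 days) depending on the target dose level".

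Section 13.1 takes as MTD the highest level with a DLT in at most one of six patients treated.

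**The concern.** A patient who stays on study, finishes cycle 1 without a DLT and never receives the cohort's venetoclax dose meets the section 11.1 definition. That patient then enters the count as a non-event at the assigned level and cannot be replaced, having not come off study.

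The plan has ordinary routes to this outcome that need not be DLTs:

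- Section 5.2.2 sets entry criteria for ramp-up.
- Table 5 holds venetoclax for grade 2 non-hematologic toxicity.
- Table 8 holds it for grade 3 neutropenia and may resume one level lower. Section 5.3 counts neutropenia as a DLT only at grade 4 for more than 5 days, or if febrile.
- Section 6.2 permits holds of up to 28 days and 50% reductions.

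With six patients deciding a level, one or two uninformative non-events can change whether it passes. The chosen level becomes the phase II target, and phase I patients at lower levels may escalate to it (section 5.1.2.1).

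**Working it through.** **1. The plan's own figures.** The escalation table in section 13.1 follows from

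P(escalate) = (1 − p)³ + 3p(1 − p)² × (1 − p)³.

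At p = 0.40 this is 0.216 + 0.432 × 0.216 = 0.309, against 0.31 printed. All nine printed values reproduce: 0.906, 0.709, 0.494, 0.309, 0.172, 0.082, 0.032, 0.009 and 0.001 for true rates of 10% to 90%. These values assume that every counted patient carries the DLT risk p of the assigned level.

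**2. The ramp-up calendar.** With weekly steps from day 8 (section 5.1.2), the first day at target is 8 + 7 × (number of earlier steps). Days at target are counted to day 49. The two cycle 1 lengths agree, since day 8 to day 49 is 42 days.

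| Level | Earlier steps | First day at target | Days at target by day 49 |
|---|---|---|---|
| 100 mg | 3 | 29 | 21 |
| 200 mg | 4 | 36 | 14 |
| 400 mg | 5 | 43 | 7 |

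At 400 mg a total ramp-up delay of 7 days moves the first target dose to day 50, past the longest stated cycle 1. The lower levels have room for delay, but a dose reduction has the same consequence at any level.

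**3. Effect on the MTD rule.** With all six patients at risk p = 0.40:

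P(at most 1 DLT in 6) = 0.6⁶ + 6 × 0.4 × 0.6⁵ = 0.0467 + 0.1866 = 0.233.

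Now let k of the six never reach the dose and carry risk q. Neither k nor q is in the documents; both are assumptions. With q = 0.10:

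- k = 1. Five at 0.40 give P(0) = 0.0778 and P(1) = 0.2592. The total is 0.0778 × (0.9 + 0.1) + 0.2592 × 0.9 = 0.311.
- k = 2. Four at 0.40 give P(0) = 0.1296 and P(1) = 0.3456. The two below dose give P(0) = 0.81 and P(1) = 0.18. The total is 0.1296 × 0.99 + 0.3456 × 0.81 = 0.408.

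The range over q, at a true rate of 40%:

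| Below dose | q = 0 | q = 0.10 | q = 0.20 |
|---|---|---|---|
| 0 of 6 | 0.233 | 0.233 | 0.233 |
| 1 of 6 | 0.337 | 0.311 | 0.285 |
| 2 of 6 | 0.475 | 0.408 | 0.346 |

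**4. What a restricted rate would estimate.** Suppose DLT-free patients below dose are dropped while ramp-up DLTs are kept. With one third below dose and q = 0.10, the expected rate is (2/3 × 0.40 + 1/3 × 0.10) / (2/3 + 1/3 × 0.10) = 0.300/0.700 = 0.429, against a true 0.40. The restricted rate errs slightly high, because patients below dose stay in only if they had an event.

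**The case against.** Several points on the other side have force.

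- **Cycle 1 length.** A reader might infer that cycle 1 closes on day 49 whatever happens, so that any one-week hold excludes 400 mg. The documents do not say this. The lengths are given as maxima, Table 9 says that cycle 1 varies in length, and section 10 allows 3 days either way during ramp-up. Completing the first cycle could be read as completing the ramp-up, and section 13.1 speaks of patients treated at a dose level. But no section defines either phrase as exposure at the assigned dose, so the gap remains.
- **Direction of bias.** A reader might infer that the DLT rate is in fact biased low. The documents give no number of patients who finished cycle 1 below dose. A DLT at any ramp-up step also counts against the assigned level, so the net bias need not be downward. What stands is that a DLT-free patient who never reached the dose adds only to the denominator.
- **Existing safeguards.** Most grade 3 or higher non-hematologic toxicity is already a DLT, as is drug-related inability to start cycle 2 after a delay of up to 21 days. Tables 5 to 8 are recommendations, and Table 8 allows growth factor without a hold. These narrow the route. They do not catch a patient who continues into cycle 2 below the assigned level.
- **Phase II monitoring.** A reader might extend the point to the phase II toxicity boundary. That boundary has its own denominator in section 13.1, patients who received at least one combination dose, and monitors the regimen as delivered. Section 11.1 does not drive it. It also offers some protection: Table 12 states a stopping probability of 0.988 at a true toxicity rate of 40%. It acts only after phase II patients are treated, and under section 13.2 the Richter's cohort has no toxicity stopping rule.
- **Timing.** Section 5 describes phase I TLS findings as already observed, so new evaluability wording may come too late to alter escalation. This is why the fix centres on re-tabulation.

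**Conclusion.** The point holds as a gap in a stated rule. Section 11.1 counts a patient without a DLT at the assigned venetoclax level on cycle completion alone, and neither the replacement rule nor section 13.4 corrects for a dose never reached. The DLT rate behind the MTD can therefore be diluted; whether it was cannot be told from the documents.

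If the true DLT rate is 40%, one patient in six below dose raises the chance of at most 1 DLT in 6 from 0.23 to between 0.29 and 0.34, and two raise it to between 0.35 and 0.48, for an assumed risk of 0 to 20% in those patients. The shift needs two conditions: that such patients occurred, and that their DLT risk was below that at the assigned dose.

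**What to change.** For the phase I data already collected, report for each level:

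- how many DLT-evaluable patients reached the assigned venetoclax dose, and for how long within the DLT window;
- the DLT rate with and without DLT-free patients who did not reach it;
- a statement that DLTs during ramp-up are kept in both rates, so the restricted rate is somewhat conservative.

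For any further dose-level evaluation, amend sections 11.1 and 5.3 so that a DLT-free patient is evaluable only after a minimum exposure at the assigned level, and otherwise can be replaced. The sponsor should set that minimum in advance. The same wording should say whether cycle 1 extends when ramp-up is delayed.

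The cost is one table from existing dosing records and a short amendment. The downside is that one or two patients might need replacing if another level is studied.

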### 2.2 Richter's Syndrome

Although the course for most CLL patients is at least initially an indolent one, it is estimated that between 1% to 11% CLL patients transform to an aggressive lymphoma. The most common transformation event, known as Richter's syndrome (RS), involves CLL transforming into diffuse large B cell lymphoma (DLBCL).

Overall, the prognosis for patients with RS is poor, though response to therapy depends on

CONFIDENTIAL

This document is confidential. Do not disclose or use except as authorized.

whether the disease is clonally related to the antecedent CLL. Patients with clonally unrelated RS have a median survival estimated at 62 months; however, about 80% of patients have clonally-related Richter's, and the median overall survival for these patients ranges from 8 to 14 months depending on the study.

Based largely on extrapolation of data from *de novo* DLBCL, the approach to RS treatment has historically been to use anthracycline containing chemotherapy, most commonly the rituximab, cyclophosphamide, doxorubicin, vincristine, and prednisone (R-CHOP) regimen. The efficacy of this approach has been evaluated in small phase 2 studies such as the German CLL2G trial, which included 15 patients with RS, and the CR rate was only 7%. Recently, data were published by the CLL group at Ohio State University on the use of a dose adjusted infusional regimen of rituximab, etoposide, cyclophosphamide, doxorubicin, vincristine, and prednisone (da-R-EPOCH) in 46 patients with RS. The CR rate of 20% was modest, and the durability of response was short. As such, novel approaches to treating Richter's Syndrome are urgently needed.

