**Accelerated ramp up for RS patients:**

CONFIDENTIAL

This document is confidential. Do not disclose or use except as authorized.

Given the potential for rapidly progressive RS, these RS patients will also have the option to undergo an accelerated venetoclax ramp-up in the inpatient setting modeled after another study of venetoclax plus chemotherapy that was recently reported ([name] et al., ICML, 2019). In that study, venetoclax was safely ramped up in a daily fashion for 20 RS patients, who were monitored closely in the inpatient setting, with no evidence of tumor lysis syndrome. The venetoclax is dosed at 20 mg for day 1, and if no TLS is observed on labs done 6-8 hours and 24 hours later, then the dose is ramped up to 50 mg on day 2, 100 mg on day 3, 200 mg on day 4, and 400 mg on day 5 if the daily labs done 6-8 hours and 24 hours later continue to show no TLS. If laboratory TLS does occur, the next day's dose will be held until there is improvement in the TLS, at which point escalation to the next dose may occur

Study visits will occur weekly through cycles 1-2, once per cycle during cycles 3-7, every two cycles from cycle 7-13, and every 3 cycles thereafter through cycle 60. After cycle 60, patients will return for study visits every six cycles until they are removed from treatment. Patients will be treated with duvelisib plus venetoclax for up to one year followed by venetoclax monotherapy until disease progression without clinical benefit, death, unacceptable toxicity, withdrawal of consent, physician/patient discussion of discontinuation based on objective disease response, or they elect to go on a new CLL or Richter's directed therapy.

CT of the neck, abdomen, pelvis and neck (CLL) or full body PET/CT (Richter's) scans will be mandatory at C4D1, C7D1, C13D1, and then at the discretion of the treating investigator or approximately every six cycles thereafter. Bone marrow biopsy will be mandatory at study entry and at the C7D1, C13D1, and C25D1 re-staging visits. Subsequent bone marrow biopsies will be performed as clinically indicated thereafter at the discretion of the treating investigator.

Patients will be evaluated for MRD negativity in the peripheral blood approximately every three months and with each bone marrow biopsy (except the baseline biopsy). MRD testing will be performed by 4-color flow cytometry with a sensitivity of  $10^{-4}$  and when possible also by ClonoSEQ (Adaptive), a next generation sequencing technology.

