**Assessments for those who discontinue treatment for reasons other than MRD negative CR/Cri or PR after C25 :**

- History and physical
- CBC differential and platelet count
- Serum Chemistry Panel including magnesium, uric acid, phosphorus and LDH
- CT or PET CT scan and response assessment as clinically indicated
- Bone marrow biopsy and aspirate as clinically indicated

After the active disease monitoring and follow up periods are complete, survival follow up data will be collected indefinitely unless one of the following occurs:

- Death
- Lost to survival follow up
- Withdrawal of consent

Survival status may be collected by phone, email, or other traditional data collection methods indefinitely.

The reason for taking a participant off study, and the date the participant was removed, must be documented in the case report form (CRF).

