**Table 9: Study Calendar:**

Cycle = 28 days (except for cycle 1 which will vary in length)	Screening**	Cycle 1 (+3 Days)					Cycle 2 (+7 Days)				Cycles 3-6 (+7 Days)	Cycles 7+ ( 2 cycles +/- 7d until C13, then q3 cycles +/-14d through cycle 60, then q6 months +/- 14 days	End of Treatment 	Active Follow Up (q3 months +/- 14 days ) and Disease Monitoring 	Survival Status	
		Day 1 	Day 2	Day 8 	Day 15 	Day 22 Day 29 Day 36 Day 43	Day 1	Day 8	Day 15	Day 22						Day 1
Procedure / Days	-28-0	Day 1 	Day 2	Day 8 	Day 15 	Day 22 Day 29 Day 36 Day 43	Day 1	Day 8	Day 15	Day 22	Day 1	Day 1				
Informed consent	X															
Duvelisib		X	X	X	X	X	X	X	X	X	X	X (through cycle 12)				
Venetoclax				X	X	X	X	X	X	X	X	X				
Survival Status																X
PK assessments (phase I study only)		X	X	X	X	X										
History and Physical Exam + Vital signs 	X	X		X	X	X	X	X	X	X	X	X	X	X	X	
Serum pregnancy test	X*															
Physical Exam Lymph node measurements		X 		X 												
Quality of life survey (appendix F)		X		X												
Concurrent Medications	X	X		X	X	X	X	X	X	X	X	X	X	X		
Urinalysis	X															
BM aspirate/biopsy 	X 										X	X	X	X		
SPEP + Immunoglobulins 	X										X	X				

CONFIDENTIAL

This document is confidential. Do not disclose or use except as authorized.

Cycle = 28 days (except for cycle 1 which will vary in length)	Screening**	Cycle 1 (+3 Days)					Cycle 2 (+7 Days)				Cycles 3-6 (+7 Days)	Cycles 7+ ( 2 cycles +/- 7d until C13, then q3 cycles +/-14d through cycle 60, then q6 months +/- 14 days	End of Treatment 	Active Follow Up (q3 months +/- 14 days ) and Disease Monitoring 	Survival Status
		Day 1 	Day 2	Day 8 	Day 15 	Day 22 Day 29 Day 36 Day 43	Day 1	Day 8	Day 15	Day 22					
Procedure / Days	-28-0	Day 1 	Day 2	Day 8 	Day 15 	Day 22 Day 29 Day 36 Day 43	Day 1	Day 8	Day 15	Day 22	Day 1	Day 1			
ECOG performance status	X						X				X	X	X	X	
EKG	X 														
Serology: SARS CoV2-,HIV, HCV, HBV 	X														
CT or PET/CT scan and Response Assessment 	X										X	X	X	X	
Hematology (CBC with differential and platelets)	X	X		X	X	X	X	X	X	X	X	X	X	X	

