***Phase II Study (Richter’s Syndrome Cohort):***

In a previous study with a commonly used chemoimmunotherapy regimen for RS, dose-adjusted EPOCH-R, the CR rate was 20%. We base this as the null hypothesis. With the addition of

CONFIDENTIAL

This document is confidential. Do not disclose or use except as authorized.

venetoclax, we hypothesize that the CR rate will be 45% or higher. Twenty patients will be enrolled and if 7 or more patients achieve CR we will regard the treatment efficacious. Conversely, if 6 or fewer patients achieve CR, we will regard the treatment inefficacious. With this design, the probability of concluding the treatment efficacious is 0.87 if the true but unknown response rate is 45% and 0.09 if the true rate is 20%. This decision rule is calculated using the exact binomial method. Table 1 below shows the operating characteristics of this design.

Table 1. Operating Characteristics

	True but Unknown CR Rate					
	20%	25%	30%	35%	40%	45%
Prob( $\geq 7$ CR in 20)	0.09	0.21	0.39	0.58	0.75	0.87

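### A Richter's patient who dies after cycle 1 but before any re-evaluation falls outside the section 11.1 response set, and no Richter's denominator or failure rule brings that patient back, so the reported CR rate and ORR can be inflated

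*Combined protocol and SAP*

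**What the plan says.** Section 11.1 (Definitions) requires measurable disease at baseline and adds that only patients who "have received at least one cycle of therapy, and have had their disease re-evaluated will be considered evaluable for response". Its note makes one exception: "Participants who exhibit objective disease progression or die prior to the end of cycle 1 will also be considered evaluable".

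The treatment plan (section 5, phase II) sets the on-treatment imaging: "scans will be mandatory at C4D1, C7D1, C13D1". In the study calendar (Table 9) the row "CT or PET/CT scan and Response Assessment" is also marked at End of Treatment. For patients who stop for reasons other than MRD negativity, section 5.6 lists "CT or PET CT scan and response assessment as clinically indicated".

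Section 13.1 gives the RS decision rule: "Twenty patients will be enrolled and if 7 or more patients achieve CR we will regard the treatment efficacious". Section 13.4 excludes from analysis only patients who never start combination therapy. Section 13.3 defines ORR as a proportion of patients without naming the set.

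Two provisions that would settle the question apply to CLL/SLL only. The sentence in 13.1 making total patients the denominator of the CR rate is under the CLL/SLL heading. The rule in 11.3.1.9 rating death from any cause as treatment failure is in the IW-CLL criteria. The Lugano table used for RS has no category for treatment failure or for a patient not assessed.

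**The concern.** The exception in 11.1 covers early failures, but it ends at the end of cycle 1 while the first planned scan comes two cycles later. The protocol gives no reason for the earlier cut-off. A death on day 20 counts against the treatment; a death on day 70 with no re-evaluation leaves the response set. Patients lost this way are failures by any clinical reading, so removing them can only raise the estimated rate.

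This matters most in RS. The protocol describes poor survival and the potential for rapid progression in this disease, and the cohort has only 20 patients, so one or two exclusions visibly move the percentage. At stake are the RS CR rate and ORR as reported, and their comparison with the 20% historical CR rate. Because the denominator is not named, it could also be chosen after the data are seen.

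**Working it through.** **1. The plan's own figures.** Exact binomial, n = 20, success if 7 or more CRs:

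- P(X ≥ 7 | p = 0.20) = 0.0867, printed as 0.09.
- P(X ≥ 7 | p = 0.45) = 0.8701, printed as 0.87.
- At 25%, 30%, 35% and 40%: 0.21, 0.39, 0.58 and 0.75, as in the 13.1 table.

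The rule counts CRs among 20 enrolled. A patient who dies unassessed is not a CR and adds nothing to the count, so both error rates stand.

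**2. Length of the gap.** Cycles are 28 days, except that cycle 1 may run to 49 (section 5.1.1). From the end of cycle 1 to C4D1 is cycles 2 and 3: 2 × 28 = 56 days. C4D1 falls between day 1 + 28 + 56 = 85 and day 1 + 49 + 56 = 106.

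**3. How an RS death in the gap, with no re-evaluation, is handled.**

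| Provision | Effect |
|---|---|
| 11.1 main rule | Not re-evaluated, so not evaluable |
| 11.1 note | Death is after cycle 1, so not covered |
| 11.3.1.9 failure rule | CLL/SLL criteria only |
| Lugano table | No applicable category |
| 13.1 total-patients sentence | CLL/SLL only |
| 13.1 RS rule | Counts CRs among 20 enrolled; names no denominator for a reported rate |
| 13.4 | Patient started the combination, so not excluded |

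Section 11.1 drops the patient. Sections 13.1 and 13.4 imply that the patient stays.

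**4. Effect on the reported rate if the 11.1 set is the denominator.** With x CRs and d such deaths, the rate is x/(20 − d):

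| d | x = 7 | x = 4 |
|---|---|---|
| 0 | 7/20 = 35.0% | 4/20 = 20.0% |
| 1 | 7/19 = 36.8% | 4/19 = 21.1% |
| 2 | 7/18 = 38.9% | 4/18 = 22.2% |
| 3 | 7/17 = 41.2% | 4/17 = 23.5% |

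**5. How many deaths could fall in the gap.** For clonally related RS, section 2.2 says "the median overall survival for these patients ranges from 8 to 14 months depending on the study". Assume exponential survival from first dose with median m months and 30.4375 days per month, so h = ln 2/(30.4375m). P(death between t1 and t2) = exp(−h·t1) − exp(−h·t2).

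| Window | m = 8 | m = 14 |
|---|---|---|
| Day 28 to 84 | 0.136 (2.7 of 20) | 0.083 (1.7 of 20) |
| Day 49 to 105 | 0.128 (2.6 of 20) | 0.080 (1.6 of 20) |

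These figures apply to clonally related disease, about 80% of RS. Section 2.2 gives a 62-month median for the rest; the same formula yields 0.020 in either window. Weighting 80/20, the highest value is 0.8 × 0.136 + 0.2 × 0.020 = 0.113 and the lowest is 0.8 × 0.080 + 0.2 × 0.020 = 0.068. Across all RS that is about 7-11%, or 1.4 to 2.3 of 20.

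All of these are upper figures for patients lost, because some would have been re-evaluated before death.

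**The case against.** The strongest reply is that section 13 never uses the 11.1 response set. The RS decision is a count among enrolled patients, and 13.4 removes only those who never start the combination. On that reading nothing is inflated. For the decision this is correct. For the reported percentage it is an inference, because 11.1 is the only place that defines who is evaluable for response, and nothing in the RS text overrides it.

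A second reply also has force: 11.1 asks for re-evaluation, not for the C4D1 scan. The calendar has weekly visits in cycles 1-2 and one per cycle in cycles 3-6, section 11.2 allows palpable nodes as measurable lesions, and a scan is marked at End of Treatment. A reader might infer that anyone who stops before C4D1 goes unscored. The documents do not support that: a patient who stops alive has a calendar scan, although section 5.6 makes follow-up scans depend on clinical indication. The firm case is death with no re-evaluation.

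A reader might also infer that the false-positive probability rises. If unassessed patients were replaced until 20 were evaluable, a true 20% CR rate would give P(7 or more) = 0.136 with 10% lost and 0.170 with 15% lost. But the documents provide for replacement only in phase I, before the end of the DLT observation period. Those figures describe a design the protocol does not contain.

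Similarly, 6/17 = 35.3% is close to 7/20 = 35.0%, but the rule has no percentage threshold. Six CRs fail it whatever the denominator.

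**Conclusion.** The point holds as a conflict between sections that can bias the reported RS CR rate and ORR upward. It does not show that the rate will be inflated: that requires both an unassessed death in the gap and use of the 11.1 set for reporting. Two such deaths would lift 7 CRs from 35.0% to 38.9%, or 3.9 percentage points.

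At most about 8-14% of clonally related RS patients would be affected, or roughly 7-11% of all RS. This rests on exponential survival from first dose at the medians in section 2.2, on a cycle 1 of 28 to 49 days, and on no re-evaluation before death. The go/no-go rule and its 0.09 and 0.87 are unaffected as written. For CLL/SLL, the total-patients denominator and the IW-CLL failure rule already largely close the gap.

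**What to change.** - **Section 11.1:** remove the end-of-cycle-1 limit from the note, so that death, progression or withdrawal at any time before the first restaging counts as non-response.
- **Section 13.1, RS cohort:** state that the RS CR rate and ORR are calculated on all RS patients who start combination therapy; that a patient without a documented CR counts as non-CR, and one without a documented response as a non-responder; and that such patients are not replaced.
- **Sensitivity analysis:** present the rate in the re-evaluated set only as a labelled sensitivity analysis.

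The sample size, the cut-off of 7 and the stated error rates do not change. The cost is wording, plus a reported rate slightly less favourable than one based on re-evaluated patients.
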